8.4.4 PHYSICAL EXAM & VITAL SIGNS

PHYSICAL EXAMINATION

The physical examination will include routine examinations for the following:

- HEENT
- Abnormalities of the extremities
- Neurologic abnormalities
- Heart/cardiovascular abnormalities
- Musculoskeletal abnormalities

CELLUTOME™ IN VENOUS LEG

- Dermatologic abnormalities
- Any other body system for which an abnormality is noted and which, in the opinion of the Investigator, is relevant to the safety of the subject or could impact safety or efficacy results for the subject; i.e., the abnormality is clinically significant.

Each abnormality will be recorded and the Investigator will record an assessment of its clinical significance.

VITAL SIGNS

The following vital signs will be collected at S1 visit only:

- Height
- Weight
- BMI calculated.
- Seated blood pressure (take after the subject has been seated for at least 5 minutes)
- Pulse
- Temperature

8.5 VASCULAR ASSESSMENTS

8.5.1 ANKLE-BRACHIAL INDEX (ABI)

Ankle Brachial Index (ABI) is the ratio of blood pressure measured at the ankle to that measured at the arm. An ABI < 0.75 indicates that there is a high probability that arterial insufficiency is present (positive predictive value 95% in a general practice population).

It should be noted that incompressible, calcified arteries may occur in diabetes causing a falsely elevated ABI, so if the subject has other signs or symptoms that could suggest peripheral arterial disease, further investigations to determine vascular status may be warranted.

A documented record of an ABI test performed using the study ulcer (target) leg, within 3 months of the first Screening visit (S1) is acceptable for the purposes of this study otherwise this must be completed in the Screening Period.

NOTE: Compression bandaging must not be applied to subjects entered onto this study unless the ABI is confirmed to be greater than 0.75.

The technique for measuring ABI explained in Appendix 19.1.

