5.2 INCLUSION CRITERIA

Potential subjects are required to meet all of the following criteria for enrollment into the study and subsequent randomization.

1. At least 18 years old.
2. Ankle Brachial Pressure Index (ABI) > 0.75. Calculations will be made using measurements from both posterior tibial and dorsalis pedis arteries as well as both arms AND/OR Skin Perfusion Pressures (SPP) greater than 30 mmHg OR Biphasic PVR OR TBI > 0.60 OR TCPO₂ > 30mmHg.
3. Presence of a VLU extending through the full thickness of the skin but not down to muscle, tendon, or bone. The largest ulcer will be designated the index ulcer and the only one included in the Study. If other ulcerations are present on the same leg the index ulcer must be 2 cm or greater in distance from the wound edge of the other ulcers.
4. Study ulcer (i.e. current episode of ulceration) had been present for at least one month (30 days) prior to the initial screening visit, and is excluded if it has undergone 12 month of continuous high strength compression therapy over its duration.
5. Study ulcer is a minimum of 2.0 cm² and a maximum of 25 cm² at the TV1 Randomization visit.
6. The target ulcer has been treated with documented full compression for at least 14 days prior to randomization.
7. Ulcer has a clean, granulating base with minimal adherent slough at the TV1 Randomization visit.
8. Females of childbearing potential must be willing to use acceptable methods of contraception (birth control pills, barriers, or abstinence). A urine pregnancy test must be administered during screening, and must be negative, for inclusion into the study.
9. Patient understands and is willing to participate in the clinical study and can comply with weekly visits and the follow-up regimen.
10. Patient has read and signed the IRB/IEC approved Informed Consent Form before screening procedures are undertaken.

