6.2 SCREENING PHASE

The subject will sign and date the ICF and HIPAA authorization (according to site practices) prior to any study-related procedures. A screening number will be assigned to each subject in successive order of entering the study after signing the ICF at each center, beginning with 001 at each site.

SCREENING VISIT – S1

The following procedures must be performed:

- Informed consent will be obtained prior to any study related procedures and the subject will sign a written Informed Consent Form
- Demographic information will be collected.
- Medical history obtained.
- Concomitant medications assessed.
- Vital signs taken.
- Physical examination performed.
- Pain assessment.
- Ulcer history recorded.
- Study Ulcer Assessments will be recorded.
- Assess signs and symptoms of clinical infection of the study ulcer.
- Vascular assessment.
- Clean the study ulcer using saline.
- Digital photo of the study ulcer.
- Perform swab on study ulcer.
- Debridement of the study ulcer if applicable.
- Application of Prisma™ or allowed antimicrobial dressing (Appendix 19.8).
- Apply multi-layer compression bandaging therapy.
- Assessment of subject's eligibility to continue on in the study.
- Schedule the next visit (S2 or TV1) in one week, if they are still eligible.

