7 STANDARD OF CARE AND CONCOMITANT MEDICATIONS

Beginning at the S1 visit, ALL subjects must have their study ulcer managed using the SOC procedures noted below.

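### Section 8.5.1 forbids compression without a confirmed ABI above 0.75, but inclusion criterion 2 accepts other perfusion tests in its place, and nothing says which rule governs

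*Combined protocol and SAP*

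**What the plan says.** **The safety note.** Section 8.5.1 states: "Compression bandaging must not be applied to subjects entered onto this study unless the ABI is confirmed to be greater than 0.75". It also says that a documented ABI on the study leg, no more than 3 months from S1, "is acceptable for the purposes of this study otherwise this must be completed in the Screening Period".

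**The eligibility rule.** Criterion 2 in Section 5.2 begins with ABI above 0.75 and continues "AND/OR Skin Perfusion Pressures (SPP) greater than 30 mmHg OR Biphasic PVR OR TBI > 0.60", ending with TCPO2 above 30 mmHg. The synopsis joins the same tests by a plain OR and adds fluorescent angiography. Neither exclusion list sets a lower limit for ABI.

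**The compression requirement.** Criterion 6 in Section 5.2 reads: "The target ulcer has been treated with documented full compression for at least 14 days prior to randomization". The S1 procedures in Section 6.2 include "Apply multi-layer compression bandaging therapy". Section 7 says that from S1 "ALL subjects must have their study ulcer managed using the SOC procedures noted below", and Section 7.3 makes compression part of every visit.

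**The stated reason for caution.** Section 2.3 reserves compression for legs without significant arterial disease and gives ABI above 0.75 as the usual threshold. Section 8.5.1 attaches to an ABI below 0.75 a positive predictive value of 95% for arterial insufficiency in general practice.

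**The concern.** The note and criterion 2 give different answers for the same leg. The note makes ABI decisive. Criterion 2 makes it optional once another test passes. Both are current operative text, and compression is the standard of care in both arms, so the question arises at S1 for any subject who qualifies on another test with a low ABI.

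What is at stake is subject safety and uniform eligibility. A site that reads criterion 2 as sufficient will compress a leg that the note says must not be compressed. A site that follows the note will screen-fail a subject whom criterion 2 accepts. With up to 30 centers, sites could handle identical subjects differently, and either choice departs from some part of the text.

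**Working it through.** No arithmetic applies, and the plan gives no figure to reproduce. The check sets the rules side by side for four kinds of subject. The test values in the first two rows are illustrative.

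| Subject | Criterion 2 | Note in 8.5.1 | Result |
|---|---|---|---|
| ABI 0.70, TBI 0.65 | Met (TBI above 0.60) | Compression barred | Rules disagree |
| ABI 0.70, SPP 40 mmHg | Met (SPP above 30 mmHg) | Compression barred | Rules disagree |
| ABI above 0.75 | Met | Compression allowed | No conflict |
| No ABI yet, another test passes | Met on that test | ABI not confirmed, so compression barred for now | Ambiguous |

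1. *Rows 1 and 2.* Sections 6.2, 7 and 7.3 call for compression at S1 and every visit once the subject is in the study. The note forbids it. The two can be reconciled only by not keeping the subject, and criterion 2 gives no such instruction.
2. *Row 4.* Section 8.5.1 asks for an ABI in the Screening Period if none is on record. Criterion 2 in Section 5.2 and the training list in Section 17.1.3 join ABI and SPP by AND/OR, which suggests that ABI may be skipped. This is unclear drafting and not a direct contradiction.
3. *Can another provision settle it?*
   - Exclusion 1 covers ulcers that the investigator attributes to arterial insufficiency. It concerns cause, is a judgement, and has no ABI cut-off.
   - Section 8.5.2 allows SPP as a vascular test and bars SPP below 30 mmHg. It does not waive the note.
   - Criterion 6 would stop a subject with no earlier compression if the note is obeyed, because 14 days of compression could not be accrued. A subject already in compression before screening can meet it.
   - Section 8.2 makes an unsuitable subject a screen failure, and Section 6.4 withdraws a subject whose ulcer cannot be dressed with compression. Both say what follows when compression is unavailable. Neither says which perfusion test decides that.
4. *Would monitoring detect it?* Section 17.9 checks the inclusion and exclusion lists. The note is in neither, so the subjects in rows 1 and 2 pass that check. Section 17.12 also asks for a general check of protocol adherence, which might find the breach, but only after compression has been applied.

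**The case against.** The strongest reply is that a site can obey every rule. Criterion 2 alone admits nobody. Section 6.2 lists the vascular assessment before compression at S1, and Section 8.2 requires suitability to be judged at each screening visit. A site that finds ABI 0.70 can withhold compression and screen-fail the subject. The note is explicit and unconditional, so the careful course is available and harm needs a site to overlook it. The 95% predictive value describes ABI alone in general practice, not a subject who has also passed TBI, SPP or TCPO2.

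Most of this stands. A reader might infer a strict deadlock, in which a subject must and must not be compressed with no way out. The documents do not support that, because screen failure and withdrawal are both provided for. Nor does the 95% figure measure the risk in the disputed subjects.

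The reply does not remove the mismatch. If the note always prevails, the alternative tests can never rescue a measured ABI of 0.75 or lower, although criterion 2 lists them as alternatives. A site that relies on the eligibility list as written would breach a safety prohibition located elsewhere.

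**Conclusion.** The inconsistency is real and needs a safety and eligibility correction. It is confined to subjects with a measured ABI of 0.75 or lower who pass another test. The case with no ABI is ambiguous only, and subjects with ABI above 0.75 are outside it.

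The conclusion rests on reading the note as unconditional and criterion 2 as a list of alternatives. The synopsis wording is plainly the latter, and AND/OR in Section 5.2 includes it.

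The number of affected subjects is not given and cannot be estimated from the documents. A reader might also infer bias in the healing comparison. That is not shown: both arms receive compression, and nothing here bears on power or error rate.

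**What to change.** Align criterion 2 to the note, in the same words in the synopsis and Section 5.2:

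*ABI > 0.75 on the study leg (calculated using the dorsalis pedis and posterior tibial arteries and both arms), from a record within 3 months of S1 or measured before compression is applied at S1. SPP, PVR, TBI, TCPO2 or angiography may be done in addition but do not replace ABI.*

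This keeps the existing measurement instruction and fixes the timing of the ABI relative to the first compression. Section 8.5.1 at present allows completion at any point in the Screening Period, and its wording should be made to match. In Section 17.1.3, change the training item to *ABI measurement, and SPP measurement if used*.

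The cost is a wording amendment with IRB approval and a notice to sites. Subjects who would qualify only on another test are lost. Their number is not given, but the present note already bars compressing them.

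Which test should govern is a clinical decision. If the sponsor's clinicians intend the alternatives to suffice, the note in Section 8.5.1 must be amended to say so, including whether a passing alternative overrides a measured ABI of 0.75 or lower. That course keeps those subjects but relaxes the present safeguard. Section 8.5.2 and exclusion 1 can stay as they are under either course. When calcified vessels are suspected, the warning in Section 8.5.1 that "incompressible, calcified arteries may occur in diabetes causing a falsely elevated ABI" remains a reason to add a second test.

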8.5.2 SKIN PERFUSION PRESSURE

Skin perfusion pressure (SPP) can also be employed to evaluate the patient’s vascular status. SPP is obtained using a Laser Doppler. Patients with SPP less than 30 mmHg have Arterial Insufficiency and are not candidates for enrollment.

8.6 PAIN ASSESSMENTS

Pain intensity of the VLU is to be assessed before any dressing changes or other wound manipulations at all screening visits, treatment visits, and at follow-up period visits.

Subject will be asked to rate his/her pain on a scale of 0 to 10 with 0 being “no pain” and 10 being the “worst pain possible”.

8.7 ULCER ASSESSMENTS

8.7.1 STUDY ULCER EXUDATE ASSESSMENTS

The Investigator will determine the amount and type, if any, of study ulcer exudate. In determining the amount of study ulcer exudate, the Investigator must take into account the amount of exudate absorbed into the study ulcer dressing. The following categories will be used to quantify the amount & describe the type of ulcer exudate:

Study Ulcer Exudate Assessment	
Volume	
 • No exudate • Minimal amount • Light (scant) or small amount • Moderate amount • Heavy/large/copious amounts
Type	
 • Not applicable: no exudate present • Serous: clear or light yellow watery plasma • Serosanguinous: pink to light-red watery plasma • Sanguineous: red with fresh bleeding • Opaque exudate: green or tan

8.7.2 STUDY ULCER INFECTION ASSESSMENTS

The presence/absence of the following signs of infection at the study ulcer site will be documented at each visit. Infection of the index wound will be assessed using the STONES method developed by Woo and Sibbald.²⁹ The wound can be considered infected when:

Study Ulcer Infection Assessment

Three of the following signs or symptoms:
 
 • Increased surface area • Increased periwound margin temperature by more than 3°F difference between 2 mirror image sites • Exposed bone or can be probed to the bone • New areas of breakdown or satellite lesions • Presence of swelling or reddened skin in periwound area • Increased wound drainage • Unpleasant, sweet, or sickening odor present 
NOTE: A wound that can be probed to the bone should warrant work-up to eliminate osteomyelitis even if other factors are absent.

INFECTION AT STUDY ULCER SITE PRIOR TO RANDOMIZATION

If the infection occurs prior to randomization *i.e.*, prior to the first Treatment Phase visit (TV1), then the subject will be ineligible to be randomized.

INFECTION AT STUDY ULCER SITE AFTER RANDOMIZATION

If infection of the study ulcer site occurs after randomization *i.e.*, after the Randomization visit (TV1), record the infection as an adverse event, and treat as appropriate with topical antimicrobial (e.g. topical silver antimicrobial) and/or oral (but not topical) antibiotics at the discretion of the investigator.

Note: topical antibiotics to the study ulcer site are prohibited

A subject with an infected ulcer that is being treated by the Investigator will remain in the study unless the situation requires an alternative methodology that violates the protocol. Antibiotic interventions will be recorded on the Concomitant Medications Form and the event will be categorized as an Adverse Event, serious if it meets the definition of that category. All subjects who show evidence of an ulcer infection must have it reported on an Adverse Event Form.

All subjects will be instructed to contact the Investigator if signs or symptoms of infection develop prior to their next scheduled visit.

During an episode of infection, the Investigator can continue multi-layer compression. However, the dressings should be changed at least every 72 hours until infection is resolved.

8.7.3 INVESTIGATOR ASSESSMENT OF STUDY ULCER CLOSURE

“**Complete healing**” of the study ulcer is defined as 100% re-epithelialization without drainage. At each visit, the investigator will assess the wound by answering the following questions:

- Study ulcer 100% re-epithelialized?
- Drainage is absent?

Both questions must be answered “yes” for the study ulcer to be considering having reached “complete closure”.

The date of complete healing is defined as the date of the first assessment of 100% re-epithelialization.

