	
CelluTome™ system at TV1, TV5 and TV9, visits plus SOC (multi-layer compression) (Group 1A) (2) SOC alone (Group 2A).
 
At TV 7, wound assessment will be carried out to evaluate wound healing in Group 2A. Subjects in Group 2A, whose percentage area reduction (PAR) is <40% will be allowed to have CelluTome™ treatment in addition to continuation of SOC and will constitute Group 2C. Group 2C subjects will receive a graft at TV7 and TV11. The remainder of Group 2A subjects will be termed Group 2B subjects. Patient codes will still remain the same to enable tracking continuity.
 
During the Treatment Phase, the wound will be swabbed for protease activity for Group 1A and 2A/B subjects: TV1 (In Group 1A this will be prior to CelluTome™ application), TV5 and TV9 visits.
 
Subjects will be evaluated on a weekly basis during the Treatment Phase. Effectiveness evaluations each week will include Investigator assessment of wound healing and measurements of ulcer size using digital planimetry. At TV4 and TV8, Prisma™ is to be applied to the study ulcer for Group 1A, 2A, and 2B subjects. Group 2C subjects will receive Prisma™ at TV10. Safety evaluations during the Treatment Phase will consist of adverse event assessments at each visit.

Dosage and Frequency of Administration
	
Epidermal grafting will be applied up to three times in Group 1A: TV1, TV5 and TV9. Group 2C subjects will receive up to two grafts: TV7 and TV11.

Duration of Study
	
A run-in period of 2 weeks followed by 12 weeks of active treatment.

Statistical Methods, Power, and Sample Size Calculations
	
Please see the Statistical Analysis Plan in the protocol.

Protease Levels
	
Absolute values of inflammatory proteases (Neutrophil elastase, MMP 8 and 9) will be measured at S1 before application of Prisma™, day 0 before application of Epidermal grafts and week 4 and 8 visits thereafter to determine the effect of protease levels on graft success for Group 1A and 2A/B subjects. The results will be blinded to the Investigators.

Key Words
	
Epidermal Grafts Chronic Wounds Clinical Trial Venous Leg ulcer Protease levels in chronic wounds

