3 STUDY OUTCOMES

Primary outcome measure is time to heal in patients treated with epidermal grafting and SOC vs. SOC alone (**Group 1A** versus **Group 2A** at 6 weeks; and **Group 1A** versus **Group 2B** at 12 weeks).

Secondary outcomes include:

1. Percentage of wounds closed at 6 and 12 weeks.
2. Correlation between protease activity and healing at 4 and 8 weeks.
3. Incidence of adverse events at 12 weeks.
4. Pain reduction between baseline and 12 weeks.
5. Cost-effectiveness (see Appendix 19.4)
6. Cost-benefit (see Appendix 19.4)

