4 STUDY DESIGN

This study is a multi-center, randomized, controlled open-label study designed to evaluate the safety and effectiveness of epidermal grafting using the CelluTome™ system plus SOC (multi-layer compression) versus SOC alone in the treatment of VLUs.

The study will have two phases: Screening and Treatment.

The Screening Phase (1 -14 days) is designed to determine whether subjects are eligible to proceed to the Treatment Phase of the study and consists of a series of screening assessments designed to determine eligibility.

At or up to 14 days before the first Screening Phase Visit (S1), written informed consent from the subject will be obtained by the Investigator or suitably qualified designee before the performance of any other protocol-specific procedure.

At the first Screening Phase Visit (S1), the Investigator will select the study (target) ulcer. Each subject will have only one VLU selected as the study (target) ulcer. In the situation where a subject has more than one VLU at the S1 visit, the Investigator will select the largest VLU that meets the eligibility criteria of the protocol as the study (target) ulcer.

The wound will be swabbed for protease activity to measure the absolute values of inflammatory proteases (Neutrophil elastase, MMP 8 and 9) before the application of Prisma™ Matrix Wound Dressing (Systagenix, San Antonio, TX).

Prisma™ is to be used during the 2 week screening phase. Prisma™ provides a moist environment at the wound surface and provides an effective barrier against common pathogens. The rationale for permitting the use of Prisma™ in subjects is to reduce the risk of infection. For subjects who are allergic to Prisma™, any of the allowed antimicrobial dressings should be used (see Appendix 19.8).

Patients whose target ulcer has been treated with compression therapy for the previous two weeks are eligible to enter the treatment phase once all of the inclusion and exclusion criteria are met. If the ulcer has not received compression, the patient should be placed in compression and enrolled in the study after 14 days of compression therapy. Ulcers that have decreased in size by more than 40% during the screening period will be excluded as a “rapid healer.”

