The Treatment Phase (TV1 to TV13) Begins with a series of assessments designed to confirm the subjects’ continued eligibility. Investigators will debride the ulcer. Subjects whose ulcers continue to meet eligibility criteria will then be randomized to one of two groups: (1) One application of epidermal microdome at day zero and standard of care (**Group 1A**) OR (2) standard of care: multi-layer compression (**Group 2A**) (see figure on next page).

During the Treatment Phase, subjects will be evaluated on a weekly basis. Effectiveness evaluations each week will include Investigator assessment of wound healing and measurements of ulcer size using digital photos.

At TV 7, wound assessment will be carried out to evaluate wound healing in **Group 2A**. Subjects in **Group 2A**, whose percentage area reduction (PAR) is <40% will be allowed to have CelluTome™ treatment in addition to continuation of SOC and will constitute **Group 2C**. **Group 2C** will receive a graft at TV7 and TV11. The remainder of **Group 2A** subjects will be termed **Group 2B** subjects. Patient codes will still remain the same to enable tracking continuity.

[figure not shown]
During the Treatment Phase, the wound will be swabbed for protease activity for **Group 1A and 2A/B** subjects: TV1 (In **Group 1A** this will be prior to CelluTome™ application), TV5 and TV9 visits.

Subjects will be evaluated on a weekly basis during the Treatment Phase. Effectiveness evaluations each week will include Investigator assessment of wound healing and measurements of ulcer size using digital planimetry. At TV4 and TV8, Prisma™ is to be applied to the study ulcer for **Groups 1A, 2A, and 2B** subjects. **Group 2C** subjects will receive Prisma™ at TV10. Safety evaluations during the Treatment

CELLUTOME™ IN VENOUS LEG

Phase will consist of adverse event assessments at each visit.

Diagram showing progress of trial and the different subjects groups. Up to 6 weeks from randomization only **Groups 1A and 2A** exist; after 6 weeks, **Groups 1A, 2B, and 2C** exist.

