6.3 TREATMENT PHASE

TREATMENT VISIT 1 (TV1) – PRIOR TO RANDOMIZATION

The following procedures must be performed:

- Pain assessment

CELLUTOME™ IN VENOUS LEG

- Assess effectiveness of compression bandaging
- Check for any changes in the subject's health and update the Medical History with any changes
- Assess concomitant medications
- Assessment of study ulcer
- Check for signs of clinical infection of the study ulcer.
- Clean the study ulcer with saline.
- Digital photo of the study ulcer
- Debridement, if required to remove non-viable tissue
- If the subject is eligible, perform the following procedures (TV1) immediately.
- If the subject is not eligible, discharge the subject from the study as a screen failure.

TREATMENT VISIT (TV1) – RANDOMIZATION

- Randomize the subject
- Perform swab on study ulcer
- If randomized to the epidermal grafting arm: Harvest epidermal grafts using the CelluTome™ device then apply the grafts to the wound bed. (Procedure detailed in Appendix 10).
- If randomized to standard of care apply provided foam to the ulcer.
- Apply multi-layer compression therapy
- Complete Quality of Life, PBI-P, and Time trade off questionnaires (see Appendices 19.5, 19.6, and 19.2)
- Schedule the next study visit one week later

TREATMENT PHASE VISITS TV2-4, 6, 8, 10, 12

The following procedures must be performed:

- Pain assessment
- Assess compression bandaging
- Assess concomitant medications
- Check for any changes in the subject's health and update the Adverse Events or Serious Adverse Events pages with any events
- Study ulcer closure assessment will be determined by a blinded observer
 - If the study ulcer is 100% re-epithelialized, the subject will be scheduled for a Pre-Healing Confirmation Visit (HCV) one week later
 - If the study ulcer is healed, no other study procedures need to be completed at this visit
- Check for signs of clinical infection. If clinical diagnosis of infection has been made, then the subject can be treated with topical antimicrobials or oral antibiotics, but topical antibiotics CANNOT be used on the study ulcer. During the time that an infection is being treated,

CELLUTOME™ IN VENOUS LEG

treatment with the IP will be stopped.

- Digital photo of the study ulcer
- Apply Prisma™ or approved antimicrobial dressing at TV4, TV8 for both **Groups 1A/2A,2B**; and at TV10 for **Group 2C**.
- Apply provided foam and multi-layer compression bandaging therapy.
- The next visit will be scheduled for one week.

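### Section 6.3 gives ulcer closure to a blinded observer and section 8.7.3 gives it to the investigator, and the plan does not say whose reading sets the time-to-heal event

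*Combined protocol and SAP*

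**What the plan says.** **Endpoint and blinding.** Section 3: "Primary outcome measure is time to heal in patients treated with epidermal grafting and SOC vs. SOC alone". It compares Group 1A with 2A at 6 weeks and with 2B at 12 weeks. Section 4: "This study is a multi-center, randomized, controlled open-label study designed to evaluate the safety and effectiveness of epidermal grafting". The one statement that blinds investigators to anything is in the synopsis entry on protease levels: "The results will be blinded to the Investigators".

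**Who judges closure.**
- Section 6.3, in all five post-randomization visit blocks (TV2-4, 6, 8, 10, 12; TV5 and TV9; TV7; TV11; TV13): "Study ulcer closure assessment will be determined by a blinded observer".
- Section 8.7.3, whose heading names the investigator: "At each visit, the investigator will assess the wound by answering the following questions". The two questions ask about full re-epithelialization and absence of drainage, and both need a yes.
- Section 4, with the same wording in the synopsis: "Effectiveness evaluations each week will include Investigator assessment of wound healing and measurements of ulcer size using digital planimetry".

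**Event date.** Section 8.7.3: "The date of complete healing is defined as the date of the first assessment of 100% re-epithelialization".

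**SAP.** Section 9.2 sets the log-rank test on time to heal. Section 9.7 lists time to heal and healed status at 12 weeks as analysis variables. Neither names the assessor.

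**The concern.** One judgement is given to two roles, and that judgement is the primary event. An analyst who follows the operative definition in 8.7.3 would take the investigator's answer. One who follows 6.3 would take the observer's. With two assessors, the rule that healing dates from the first assessment is itself ambiguous: it could mean the first by either person, by the observer, or by the investigator.

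Full re-epithelialization and absence of drainage are visual judgements. Nothing in the plan conceals treatment arm from the investigator. If that reading sets the event, a lean towards calling closure sooner or more often in one arm enters the log-rank test as a treatment effect. If the choice of reading is left until results are visible, the choice can also be influenced by those results.

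**Working it through.** **1. The texts side by side**

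| Place | Who | What they do |
|---|---|---|
| 6.3, TV2 to TV13 | Blinded observer | Determines closure |
| 8.7.3 | Investigator | Answers the two closure questions at each visit; closure and its date are defined here |
| 4 and synopsis | Investigator | Weekly assessment of wound healing |
| 9.2, 9.6, 9.7 | Not stated | Use time to heal and healed status |

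The direct conflict is between 6.3 and 8.7.3. Section 4 and the synopsis are consistent with 8.7.3 but do not say that the investigator determines closure. The criteria also differ. Section 6.3 books the confirmation visit on re-epithelialization alone. Section 8.7.3 adds absence of drainage but dates healing by re-epithelialization.

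**2. The plan's own power figure**

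Inputs from section 9.3: 113 control and 112 treatment subjects, control healing 0.5 at 12 weeks, hazard ratio 1.74, weekly dropout 0.033 and 0.0083, two-sided 0.05.

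- Control hazard: ln 2 / 12 = 0.0578 per week.
- Expected events with exponential healing and dropout: 47.6 control + 75.4 treatment = 123.0.
- Schoenfeld: Φ(√(123.0/4) × ln 1.74 − 1.96) = Φ(1.11) = 86.7%. A Lakatos-type calculation gives 85.7% and Freedman's formula 85.0%.

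The stated 86.1% reproduces. Naming the assessor does not change it.

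**3. What an assessor lean could do (illustration)**

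The size of the lean is an assumption. Take no true effect, 50% healing, and over-calling by d in one arm. With z = d / SE, P(reject) = Φ(z − 1.96) + Φ(−z − 1.96).

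*All of 2A (113) against 112.* SE = √[0.25 × (1/113 + 1/112)] = 0.0667.
- d = 0.05: z = 0.75, P = 0.1131 + 0.0034 = 11.7%.
- d = 0.10: z = 1.50, P = 0.3228 + 0.0003 = 32.3%.

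*Group 2B against 112.* Section 5.1 expects 30% of 2A to move to 2C, so 2B is 113 × 0.70 ≈ 79 before dropout. SE = √[0.25 × (1/79 + 1/112)] = 0.0735.
- d = 0.05: z = 0.68, P = 0.1004 + 0.0041 = 10.5%.
- d = 0.10: z = 1.36, P = 0.2747 + 0.0004 = 27.5%.

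*Cross-check with the planned log-rank test.* With 113 and 112 subjects and the section 9.3 dropout rates, apparent healing of 55% against 50% is a hazard ratio of ln 0.45 / ln 0.50 = 1.15. For 60% it is ln 0.40 / ln 0.50 = 1.32. The rejection rates are about 11% and 31%, so the simpler formula is adequate here.

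*Smaller leans.* On the same log-rank basis, inflating the apparent graft-arm hazard by 1.05, 1.10, 1.20 or 1.30 (apparent healing 51.7%, 53.3%, 56.5% or 59.4%) gives 5.7%, 7.7%, 15.6% or 27.9%.

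The 2B figures keep 50% healing only to show the effect of the smaller group. Removing the slow healers from 2A would change its true healing rate, which is a separate matter.

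**The case against.** The strongest reply is that the plan already leans towards the blinded observer. Section 6.3 says five times that the observer determines closure, whereas 8.7.3 says only that the investigator assesses the wound. Both could happen at one visit, with the observer's reading decisive. That reading is possible, but no available text states it or ranks the two. The only definition of closure and of its date sits under the investigator's heading.

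A second reply points to later checks: a confirmation visit a week after re-epithelialization (6.3), confirmation about two weeks after healing (9.6, 9.7) and weekly photographs (6.1). These make a sustained over-call of 5 to 10 points less plausible. They do not name the assessor, and 8.7.3 still dates healing from the first assessment, so they reduce the risk without settling whose reading counts.

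A third is that the size of bias is assumed. That is correct, and mild leans do little, as the smaller cases above show.

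Two stronger readings are tempting and should not be made.
- A reader might infer that the investigator judging closure also applied the graft. Section 6.3 names no one for harvesting or application, and the site initiation list in 17.1.3 mentions only physician training. The argument needs only that the investigator can know the arm, which is a fair inference from the open-label design.
- A reader might take section 4 and the synopsis as giving closure to the investigator. They mention only weekly assessment of healing.

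**Conclusion.** The inconsistency is in current text and reaches the primary endpoint: the plan does not say whose reading sets the time-to-heal event. Following 8.7.3 as written would let an assessor with no stated blinding to arm set that event, although 6.3 already requires a blinded one.

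The bias is conditional. It arises only if the investigator's reading governs, and the documents do not support saying that the trial is biased as designed. Under the stated assumptions (no true effect, 50% healing, a lean in one arm only), the false-positive rate rises from 5% to about 10–12% for a 5-point lean and about 28–32% for a 10-point lean. These figures show sensitivity and do not predict what would happen.

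One limit applies: a part of the document just before section 9.1 was not available, so the statement that the SAP is silent covers the available text. The conflict between 6.3 and 8.7.3 stands regardless.

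**What to change.** State in 8.7.3, section 4, the synopsis and the SAP that:

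- the blinded observer required by 6.3 determines the closure event and its date for all healing endpoints, using both questions in 8.7.3;
- the investigator's answer is recorded as supportive only and is not used to settle disagreements;
- the observer is kept blind to arm by a described procedure. The documents do not say who the observer is or how blinding is maintained. The description should cover the donor site on the inner thigh (19.10), which an observer who sees the subject might notice.

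Bring the closure criterion in 6.3 into line with 8.7.3 at the same time. Settle all of this before any comparison of healing by arm.

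The cost is protocol and SAP wording plus a short account of the blinding procedure. Because 6.3 already calls for the observer, the role is not new, but the documents do not show what staffing sites have in place for it. Sample size and power are unchanged.
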